7.5 Follow-up for Adverse Events

If AE is still present at the time it is reported, it will be re-assessed one week later either in person, via online survey or via phone. If the AE is still present 2 weeks after last day of study participation, it will be considered stable, and we will not continue assessments. Safety review by Independent Monitoring Committee will occur if resolution of AE has not occurred 2 weeks after discontinuing study drug (due to study completion or dropout) and AE is considered to be related to study intervention (possibly, probably or definitely) by study PI and the Independent Clinical Monitor.

7.6 Safety Monitoring

The Principal Investigator has appointed an Independent Monitoring Committee for this research study. The members include the following: [name], M.D., a child psychiatrist with expertise in adolescents at risk for self-harm from University of Pittsburgh; [name], a child psychiatrist from Stanford University with expertise in adolescent depression and clinical trials; [name], an Associate Professor of biostatistics from Columbia University Medical Center. The Committee will meet for the first time 6 months after the start of study enrollment, and then again one year later. The PI has also assigned [name] [name] to act as the Independent Clinical Monitor to assist the PI in (1) assessing and characterize adverse events (2) determining whether study drug should be reduced or discontinued, and (3)

determining whether the participant should be withdrawn from study procedures.

8. INTERVENTION DISCONTINUATION

The intervention will be discontinued in the following circumstances:

- If the participant is unable to tolerate the study medication due to side effects or allergic reaction, even after decreasing the dose, as determined by a conversation between the PI (or delegate) and the participant.
- If the participant elects to no longer take the study medication.
- If the participant becomes actively suicidal with intent and plan, and cannot agree to a safety plan engaged by study team (see Supplement IV).
- If the participant or parent of minor participant withdraws consent.
- If the participant becomes pregnant.
- If the IMC or the Medical Monitor recommend participant withdrawal due to safety concerns.

Discontinuing the intervention will also be considered in the following circumstances:

- If a participant engages in NSSI with significant tissue damage that requires urgent/emergency medical care, study staff will assess safety of participant and engage participant (and parents of minors) in a safety conversation to discuss how to increase safety in the home, whether hospitalization is needed, and whether continuing in the study is appropriate (See Supplement IV). If it is deemed safe by study staff with respective input from NCCIH, FDA, Advarra IRB and/or IMC when necessary and participant (and parents of minors) desire to continue, remaining study visits will be completed.
- If a participant fails to adhere to protocol requirements, study staff will assess safety of participant with respect to protocol deviation(s) and engage participants (and parents of minors) in conversation to discuss their safety and if continuing in the study is appropriate. If it is deemed safe by study staff with respective input from NCCIH, FDA, Advarra IRB and/or IMC when necessary and participant (and parents of minors) desire to continue, remaining study visits will be completed.
- Changes to psychiatric medications during the study are strongly discouraged, and we will ask participants to promptly notify us of any changes. If such changes occur, the Principal Investigator and co-investigators [name], [name] or [name] will review the relevant information and potential interactions. If it is determined that the new medication(s) raise potential safety concerns while being taken with NAC, the participant will be advised to stop taking study drug and still complete study visits as planned. Otherwise, the participant will continue. These changes will be documented and incorporated into sensitivity analyses as described in section 9.6.

For all above withdrawal circumstances, participant contribution to subsequent data

collection will depend on safety considerations, participant interest and the adherence of each participant (Section 5.3).

9. STATISTICAL CONSIDERATIONS

9.1 General Design Issues

The goals of this study are to test whether significant change can be found in candidate biological signatures after 4 weeks of oral NAC. Three groups are used to compare pre-post treatment changes in those who received NAC 5400mg/day, 3600mg/day, or PBO.

Primary Hypothesis:

- 1) NAC high dose and/or NAC low dose (but not PBO) will increase cortical GSH by at least 5%

Secondary Hypotheses:

- 1) NAC high dose and/or NAC low dose (but not PBO) will decrease cortical GLU by at least 5%
- 2) NAC high dose and/or NAC low dose (but not PBO) will increase blood GSH/GSSG by at least 50%
- 3) NAC concentrations (using data from both dose groups) will be correlated with clinical and neuroimaging outcomes.
- 4) NAC high dose and/or NAC low dose (but not PBO) will increase resting-state functional connectivity between amygdala and insula
- 5) NAC high dose and/or NAC low dose (but not PBO) will increase ACC GABA.
- 6) NAC high dose and/or NAC low dose (but not PBO) will increase antioxidant protein levels (catalase and heme oxygenase-1 [HO-1]).
- 7) Higher-dose NAC will show larger changes in all of the biological signatures listed above compared to lower-dose NAC
- 8) While both NAC doses will be acceptable to most patients, lower-dose NAC will be better tolerated than higher-dose NAC.

Primary outcome measures:

- 1) GSH concentration in ACC

Secondary outcome measures:

- 1) Blood GSH/GSSG (the reduced-to-oxidized GSH ratio in blood)
- 2) Glu concentrations in ACC
- 3) Tolerability of NAC as measured using a side effects checklist
- 4) Pharmacokinetic analysis of NAC and its metabolites, CYS and GSH
- 5) Antioxidant protein levels (catalase and heme oxygenase-1 [HO-1]) for which

previous studies have shown increases following NAC treatment.

- 6) GABA concentrations in the ACC. Our pilot study found a significant increase in GABA levels after 28 days of oral NAC (6000 mg/day) ([name] et al. 2018).
- 7) Functional connectivity between amygdala and insula. Our pilot study showed that after treatment with oral NAC (3600 mg/day), participants with NSSI showed an increase in amygdala functional connectivity in a cluster that included the bilateral insula.

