1. STUDY OBJECTIVES

1.1 Primary Objective

To test the hypothesis that oral NAC treatment (but not placebo) will lead to at least a 5% increase in glutathione (GSH) concentrations in the anterior cingulate cortex as measured by magnetic resonance spectroscopy (MRS) in a study of 36 adolescents and young adults with NSSI.

We will test two NAC doses (3600mg and 5400mg). Dose superiority will be defined both by change in GSH and by tolerability. Specifically, the superior dose will be the one which showed capability of achieving the greatest increase in GSH in the ACC as measured by MRS, and where no more than 20% of subjects at that dose discontinue or diminish their dose due to medication adverse effects (See section 5.1 for adverse effects and diminishing dose). (In other words, no less than 80% of subjects at a dose can discontinue or diminish their dose due to adverse effects in order to qualify as a superior dose.)

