9.2 Sample Size and Randomization

The sample size (n=12 per group) was selected based on calculations on biosignature data from the oral NAC pilot study in adults with either Parkinson's disease (PD; n=5) or healthy controls (HC; n=3). Using variability estimates from this study, we found that with groups of 11 (assuming one drop-out per group), we would have 80% power to show a significant ($\alpha=0.0167$, Bonferroni corrected for 3 pairwise comparisons) effect of NAC high vs. NAC low vs. PBO on our primary outcome of brain GSH if the variability is similar to healthy controls seen in our pilot work (detectable mean group difference in pre-dose to post-dose percent change of 2.95%, expected mean group difference ~4.83%). The data collected in the R61 will serve to provide the variability information needed to design a future, confirmatory clinical trial.

Treatment Assignment Procedures

Randomization and Double-Blind: Participants who meet criteria for entry into the study (based on the online screen and the clinical interview) and who provide consent will be randomized to active NAC low dose versus NAC high dose versus PBO (1:1:1). We will implement an adaptive randomization procedure called minimization. The purpose of the procedure is to ensure that the 3 groups are similar with respect to key demographic and clinical variables such as age, NSSI severity and medication use. See Section 6.2.2 for a complete description of the randomization procedure.

All participants, family members, and study staff (including the study statistician) will be blinded to treatment assignment. The research pharmacy, IDS, will be the only unblinded entity. See Section 6.2.2 for a complete description of the blinding (and unblinding) procedures.

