9.6 Data Analyses

To address the study objectives, we will quantify the within-person percent change in proposed primary biological signature: brain GSH. We will fit a general linear model with brain GSH as dependent variable with group (NAC high vs NAC low vs PBO) as the predictor variable of interest. Since we apply a minimization procedure to ensure that groups are similar on key demographic and baseline clinical variables (age, baseline NSSI severity, presence of concurrent psychotropic medication), as is typically done in a large clinical trial we will not include covariates. Should the primary outcome values be highly skewed, we will use non-parametric tests instead to compare groups. We will use the standardized Wilcoxon test statistic with the Dwass, Steel, Critchlow-Fligner (DSCF) multiple comparison analysis. This analysis takes each pair of groups, one pair at a time (high NAC vs. low NAC; high NAC vs. placebo; low NAC vs. placebo), computes a Wilcoxon test statistic to compare the two groups in that pair, and obtains a pvalue that is analogous to Tukey's control of family-wise Type I error (the test statistic is scaled to Tukey's studentized range distribution) (Hollander and Wolfe, 1999). This analysis to compare the 3 treatment groups on the primary outcome will adjust type I error using Tukey's procedure for the 3 pairwise comparisons among the 3 groups. Tukey's procedure is less conservative than the Bonferroni adjustment used in the sample size/power

calculation, hence we expect slightly higher power than planned. We will quantify the effect size of each group's change to determine next steps with the research.

To assess the robustness of our conclusions about the primary outcome to participants whose medical profile changes during the course of active treatment in our study, we will conduct sensitivity analyses. For example, if participant(s) need to have a change in their non-study medications during our study, they will remain in the study but the changes in medications will be noted in the study database. We will repeat our primary analysis excluding such people to see if our conclusions remain the same. We note, however, that this analysis is not protected from bias by the randomization.

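### The primary hypothesis is a GSH rise of at least 5% in one or both NAC arms and not on placebo, but the plan tests and powers only a non-zero difference between groups, so a significant result does not settle it

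*Combined protocol and SAP*

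**What the plan says.** Section 1.1 gives the primary objective as "To test the hypothesis that oral NAC treatment (but not placebo) will lead to at least a 5% increase in glutathione (GSH) concentrations". Section 9.1 repeats it as the numbered primary hypothesis: "NAC high dose and/or NAC low dose (but not PBO) will increase cortical GSH by at least 5" percent. Both describe an arm's own change against a threshold, and in 9.1 one NAC arm is enough.

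Section 9.2 plans on a contrast between groups. With 11 analysed per group, alpha 0.0167 per comparison and 80% power, it gives a "detectable mean group difference in pre-dose to post-dose percent change of 2.95%, expected mean group difference ~4.83" percent.

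Section 9.6 fits a general linear model with treatment group as the predictor, and states: "This analysis to compare the 3 treatment groups on the primary outcome will adjust type I error using Tukey's procedure". There is a fallback: "Should the primary outcome values be highly skewed, we will use non-parametric tests instead to compare groups", using pairwise Wilcoxon statistics with the DSCF adjustment. The one sentence about an arm's own change is "We will quantify the effect size of each group's change to determine next steps with the research".

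The dose rule in Section 1.1 uses the greatest GSH increase together with tolerability, and sets no 5% minimum.

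Two secondary hypotheses in Section 9.1 have the same form: "NAC high dose and/or NAC low dose (but not PBO) will decrease cortical GLU by at least 5" percent and "NAC high dose and/or NAC low dose (but not PBO) will increase blood GSH/GSSG by at least 50" percent. Section 9.6 analyses both with similar linear models, under a Holm adjustment across group comparisons and secondary outcomes.

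**The concern.** The hypothesis and the test differ in two respects. The hypothesis concerns the change within an arm, and the test concerns the difference between arms. The hypothesis sets the value at 5%, and the test sets it at zero. No section links the two, and no section says how the placebo half of the hypothesis is to be judged.

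A significant group difference and a rise of at least 5% can therefore disagree, and the plan does not say which one decides the primary hypothesis. The same data could be reported as meeting it or as missing it, with the choice made after the results are known. This matters because Section 9.6 uses the size of each group's change to decide what research follows.

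**Working it through.** **Inputs.** From Section 9.2: n = 11 per group, alpha 0.0167 (taken as two-sided), power 80%, detectable difference 2.95 points, expected difference about 4.83 points. From Section 9.6: three groups, Tukey adjustment. The outcome is taken to be within-person percent change, as Sections 9.2 and 9.6 indicate. The plan gives no SD.

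**Step 1: the SD implied by the plan's own figures.** By the normal approximation, SD = 2.95 / [(2.393 + 0.842) × √(2/11)] = 2.95 / (3.235 × 0.4264) = 2.14. With the noncentral t it is 1.98 (20 df) or 2.04 (pooled, 30 df). The SD is back-solved, so the 80% is returned by construction. The figures are coherent with each other but not independently verified. SD 3, 4 and 5 are used below as an assumed range.

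**Step 2: precision.**
- Own-arm 95% interval, half-width 2.042 × SD/√11: 1.22 at SD 1.98, 1.32 at 2.14, and 1.85, 2.46 and 3.08 at SD 3, 4 and 5.
- Difference significant under Tukey when it exceeds 2.465 × SD × √(2/11): 2.08, 2.25, 3.15, 4.20 and 5.26 at the same SDs.

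Suppose the observed placebo change is zero. At SD 1.98 an observed rise above 2.08 is significant, and an observed rise below 5 − 1.22 = 3.78 has its interval wholly below 5%. Between 2.08 and 3.78 both are true. At SD 3 the two limits meet (3.15 and 5 − 1.85 = 3.15), so the overlap then depends on chance variation in the placebo mean and in the SD estimate.

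**Step 3: how often the two readings disagree.** Noncentral t and simulation, true placebo change assumed 0. Joint means NAC-placebo significant and the NAC arm's own interval wholly below 5%.

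| SD | Rise 2.95: significant | of those, own interval below 5% | Joint (product) | Rise 4.83: significant | Joint | Own interval includes 5% |
|---|---|---|---|---|---|---|
| 1.98 | 0.840 | 0.897 | 0.753 | 0.999 | 0.045 | 0.94 |
| 2.14 | 0.774 | 0.832 | 0.644 | 0.997 | 0.042 | 0.94 |
| 3 | 0.448 | 0.380 | 0.170 | 0.898 | 0.019 | 0.95 |
| 4 | 0.248 | 0.110 | 0.027 | 0.644 | 0.005 | 0.95 |
| 5 | 0.156 | 0.034 | 0.005 | 0.432 | 0.001 | 0.95 |

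The value 4.83 is given as a group difference. It equals an arm's own rise only if placebo does not change.

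**Step 4: the other direction.** If NAC truly rises 5% and placebo 3%, the between-group test at alpha 0.0167 and SD 1.98 is significant in only 42% of trials, although the NAC arm reaches the threshold and placebo does not.

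**The case against.** The strongest reply is that 5% is a predicted size and not a margin to be excluded. Section 9.1 opens with the aim of finding significant change and says that the three groups serve to compare pre-post changes. The placebo clause is naturally served by a between-group test. Section 9.2 leaves confirmation to a later trial. Nowhere does the plan promise an interval wholly above 5%, and a comparison of the observed mean with 5% would fit the text equally well.

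That is fair, and it limits the point. It does not remove it, because the plan does not state that reading either. Under it the two criteria still part: at a true rise of 4.83%, SD 1.98 and flat placebo, the test at alpha 0.0167 is significant in 99.8% of trials, and in 61% of those the observed rise is below 5%.

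Four stronger inferences are not supported:
- That each NAC arm must reach 5%. Section 9.1 says one or both.
- That an arm's own change is never examined. Section 9.6 quantifies it. What is missing is an interval and a stated reading against 5%.
- That the 80% power is wrong. It is coherent for a 2.95-point difference from zero; it answers a different question.
- That a significant result would usually come with a rise clearly below 5%. This holds at a true rise of 2.95% and SD about 2. It becomes uncommon as the SD grows, and rare at 4.83%.

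**Conclusion.** The mismatch is real and does not depend on the SD. The hypothesis is a rise of at least 5% on NAC and not on placebo, while the test and the power concern a non-zero difference between groups. A significant result would not establish the hypothesis as worded.

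The practical size does depend on assumptions: a back-solved SD and a placebo change of zero. At a true rise of 2.95%, a significant result with the arm's own interval wholly below 5% occurs in about 64-75% of trials over the implied SD range, and in 17%, 3% and 0.5% at SD 3, 4 and 5. At 4.83% it occurs in at most about 4.5%, and the usual finding about 5% is an inconclusive one. A reader should not infer that significance is assured at 4.83%: it exceeds 99% at SD about 2, but is 90%, 64% and 43% at SD 3, 4 and 5.

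The same structural gap applies to the 5% Glu and 50% blood GSH/GSSG hypotheses. No figures were worked for those.

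**What to change.** - **Sections 1.1, 9.1 and 9.6:** state that the tested primary claim is a NAC minus placebo difference in percent change above zero, within the three planned Tukey-adjusted pairwise comparisons. Keep high versus low dose among them, and do not call the claim confirmatory.
- **Section 9.6:** keep 5% as a pre-stated benchmark. Report each arm's mean percent change, placebo included, with a 95% interval read as below, including or above 5%, next to the simultaneous intervals for the differences. In the skewed-data branch report each arm's median change with an interval, since DSCF p-values cannot be read against 5%.
- **Section 9.2:** say that the 80% power is for a 2.95-point difference from zero and not for showing a rise of at least 5%. Stating the pilot SD would let a reader check it.
- **Sections 1.2, 9.1 and 9.6, secondary outcomes:** add the same within-arm reading for Glu (5%) and blood GSH/GSSG (50%), keeping the Holm adjustment for their tests.

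The cost is wording and one table of within-arm results, with no change to the test or the sample size. The drawback is that at the planning effect most trials would be reported as inconclusive about 5%.

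Separate item: Section 1.1 gives the tolerability criterion for the superior dose in two opposite ways. One sentence allows at most 20% of participants at a dose to stop or reduce it because of adverse effects; the restatement that follows puts the share at no less than 80%. The two sentences must be reconciled.

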9.2 Sample Size and Randomization

The sample size (n=12 per group) was selected based on calculations on biosignature data from the oral NAC pilot study in adults with either Parkinson's disease (PD; n=5) or healthy controls (HC; n=3). Using variability estimates from this study, we found that with groups of 11 (assuming one drop-out per group), we would have 80% power to show a significant ($\alpha=0.0167$, Bonferroni corrected for 3 pairwise comparisons) effect of NAC high vs. NAC low vs. PBO on our primary outcome of brain GSH if the variability is similar to healthy controls seen in our pilot work (detectable mean group difference in pre-dose to post-dose percent change of 2.95%, expected mean group difference ~4.83%). The data collected in the R61 will serve to provide the variability information needed to design a future, confirmatory clinical trial.

Treatment Assignment Procedures

Randomization and Double-Blind: Participants who meet criteria for entry into the study (based on the online screen and the clinical interview) and who provide consent will be randomized to active NAC low dose versus NAC high dose versus PBO (1:1:1). We will implement an adaptive randomization procedure called minimization. The purpose of the procedure is to ensure that the 3 groups are similar with respect to key demographic and clinical variables such as age, NSSI severity and medication use. See Section 6.2.2 for a complete description of the randomization procedure.

All participants, family members, and study staff (including the study statistician) will be blinded to treatment assignment. The research pharmacy, IDS, will be the only unblinded entity. See Section 6.2.2 for a complete description of the blinding (and unblinding) procedures.

9.3 Definition of Populations

The Intent to Treat population will include all those who completed both baseline and 4-week MRI scans and blood draws, even those who discontinued the study medication due to intolerance or other reasons. The Per-Protocol analysis population will consist of only those subjects who completed all procedures.

9.4 Interim Analyses and Stopping Rules

The following safety findings would prompt temporary suspension of enrollment and

study intervention until a complete safety review is convened:

- Suicide attempt in greater than 20% of participants that have received study intervention beginning when at least 10 participants have received study intervention.
- Suicide attempt in greater than 30% of participants that have received study intervention when between 1 and 9 participants have received study intervention.
- SAE in greater than 30% of participants to receive study intervention
- SAE occurrence in first 3 participants to receive study intervention
- AE indicating anaphylaxis to study intervention in at least 30% of participants to receive study intervention beginning when 10 participants have received intervention
- Suicide completion in at least 2 participants to receive study intervention
- Anything else deemed a safety risk to participants by the investigator or the IMC

“Study intervention” refers to any or all 3 of the treatment groups. The following safety findings would prompt an ad hoc safety review without suspension of enrollment and study intervention:

- NSSI frequency in past month increase of 100% in any single participant as determined by SITBI (question 148), comparing Day 1 and Day 28 – 32 assessments.
- Average NSSI frequency in past month increase of 50% during study enrollment as determined by SITBI (question 148, NSSI section, “How many times in the past month?”) comparing Day 1 to Day 28 - 32 measurement beginning when 5 participants have received study intervention.
- Suicide completion in 1 participant to receive study intervention

A safety review will be carried out by the Independent Monitoring Committee and its occurrence would be reported to Advarra IRB and NCCIH. Safety findings such as those listed above will be presented to Independent Monitoring Committee to review the events by blinded group to determine whether there are statistical as well as clinical concerns. The objective of the safety review is to determine whether the study or intervention (NAC) for an individual or for the study cohort should continue per protocol, proceed with enhanced monitoring, be further investigated, be discontinued, or be modified and then proceed. Suspension of enrollment is a potential outcome of a safety review.

Outside of safety reviews, no interim analyses are planned for this study.

